2.1.3 Efficacy endpoints

2.1.3.1 Primary efficacy endpoint(s)

The primary efficacy endpoint will be the Overall Response Rate (ORR) defined as the proportion of patients with confirmed complete response (CR) or confirmed partial response (PR) as Best

Overall Response (BOR), assessed by the Investigator (based on RECIST 1.1), relative to the total number of patients in the efficacy population (see [Section 2.3.1](#)). Confirmation of objective responses will be performed by repeat tumor imaging (Computed Tomography [CT] scan, MRI) at least 4 weeks after the first radiological documentation of response.

Tumor assessments will be performed every 6 weeks (ie, every 2 cycles) during the treatment period and every 6 weeks during the follow-up period if a patient discontinues treatment prior to radiologic disease progression.

Tumor assessments after the initiation of post-treatment anti-cancer therapy will be excluded from the determination of Best Overall Response in a patient. See [Appendix B](#) (Determination of tumor response) for details.

Best Overall Response

BOR is the best tumor response observed from first study treatment infusion until disease progression, death or initiation of post-treatment anti-cancer therapy, whichever occurs first.

Primary ORR analysis can be performed when all patients treated in Part 2a and Part 2b have had at least 4 postbaseline tumor assessments, experienced confirmed objective response, or have discontinued the study for any reason. However, if the primary criteria of 7 responders is either met or not met with certainty at the end of the Part 2a in the selected dose when all patients have had 2 postbaseline tumor assessments, experienced confirmed objective response, or discontinued the study for any reason and when all the patients of the Part 2b have had 2 postbaseline tumor assessments, experienced confirmed objective response, or discontinued the study for any reason, analysis may be done at that time instead.

Best tumor shrinkage

For patients with measurable disease, the best tumor shrinkage will be defined by the best relative change from baseline as follows:

$$Y = 100 \times \frac{Y_{smallest} - Y_{baseline}}{Y_{baseline}}$$

Where Y is the sum of longest diameter of the target lesions.

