2.5.3 Data handling conventions for secondary efficacy variables

Valid/Evaluable tumor assessment:

A valid post-baseline tumor assessment is one for which the derived “overall objective response” is not “NE” (not evaluable) as per RECIST 1.1 criteria. If the date of assessment is missing, the tumor assessment is not valid.

In case of missing scans, i.e. if one lesion is not evaluated/missing for a given tumor assessment, the overall response should generally be NE unless there is a clear evidence of progression (independently of the missing lesion).

Date of last valid tumor assessment (different from PD): if several scans are performed at different dates for a given tumor evaluation reported in the e-CRF, the date of the last valid tumor assessment is the date of latest scan.

Date of disease progression determination:

- PD by New lesion: for progression based on a new lesion, the date of progression is the date of the first observation that the new lesion was detected,
- PD by target lesion: if multiple assessments based on the sum of target lesion measurements are done at different times, the date of progression is the date of the first radiological measurement,
- PD by non-target lesion: if the first documented progression is based on a non-target lesion alone, the date of PD is the initial date at which unequivocal progression is associated with non-target disease,

- PD by a combination of factors: if the first documented progression is based on a combination of target and new and/or non-target disease, the date of PD shall be the earliest date associated with any of the contributing factors.

The rules to determine date of progression are consistent with FDA recommendation described in “Guidance for Industry Clinical”

- Efficacy response variable: when a proportion is calculated for a binary response variable (eg, response rate), the denominator is based on the total number of patients in the analysis population used for the summary. There can be 3 observations: Yes, No and Nonevaluable (or missing). For the patients with non-evaluable outcomes, the default rule is that the patients will be treated as “no events”.
- Time to event data: missing outcomes due to different reasons will be handled using adequate censoring rules. The censoring rules are specified as part of the definition of the analysis variables in corresponding section.
- Handling of missing/partial death dates:

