Appendix B Determination of tumor response

The overall response at each time point and the best overall response will be determined by the Investigator derived from the tumor measurements data according to RECIST 1.1 criteria ([Appendix C](#)) using the following algorithm.

- Overall Response:

Overall response, or integrated response, will be determined by the investigator using assessments of target, non-target and new lesions according to RECIST 1.1. See [Appendix C](#) for details.

- Confirmation:

According to RECIST 1.1 a confirmed CR or PR will be based on two tumor assessments at least four weeks apart as follows: if a CR or PR outcome is reported, then a second tumor assessment with CR or PR at least four weeks later is needed for confirmation, regardless of how many “unknown/not applicable/missing/non evaluable” tumor assessments are in between the two outcomes.

- Best Overall Response (BOR) :

In general, a patient’s best tumor response will depend on the achievement of both: documented tumor measurement assessments and confirmation of the tumor response by RECIST1.1 criteria. For each patient the BOR will be derived based on the following algorithm:

– a) PR/CR will be determined based on confirmed PR and confirmed CR described in the algorithm above.

– b) SD and PD will be determined from the overall tumor response at each timepoint. If SD is the overall response and it occurs less than 35 days from first study administration, then overall response will not be SD. For patients who stop the treatment due to a symptomatic deterioration or death, without any other tumor assessment before the symptomatic deterioration or death, then the BOR will be considered as NE. These cases will be described separately as patients in early progression or early death.

If PD is the overall response and it occurs less than 42 days from the first study administration, then the best overall response is PD.

– c) Convention for PD after several NE cycles: in the case where the assessment at study entry is followed by several visits (or cycles) with no assessment (or only NE assessments or SD <35 days from first study administration) for more than twice the periodicity of tumor assessments (ie, for more than 42 days), and the next assessment is PD, the best overall response will be NE. If the PD occurs within this period of time, the best overall response will be PD.

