Using the outcome from a), b) and c) above, the BOR will be determined based on the following order of Overall Responses: CR, PR, SD, PD and NE.

In the BOR determination, tumor assessments performed after a patient started post-treatment anti-tumor therapy will not be considered. The date of post-treatment anti-tumor therapy for a patient will be the earliest date among the dates for “Post Treatment Anti-Cancer Drug Therapy”, “Post Treatment Radiation Therapy” and “Post-Treatment Anti-Cancer Surgery” for target and non-target lesions identified at baseline. Assessments performed after the earliest post-treatment anti-tumor therapy will be excluded from the determination of BOR. If, in the same tumor evaluation period, several assessments are performed before the first post-treatment anticancer therapy and several assessments are performed afterwards, the disease assessment will be included in the determination of BOR.

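### SAP Appendix B keeps a tumor evaluation that straddles the start of new anticancer therapy without limiting it to the pre-therapy scans, so a post-therapy scan can confirm a primary-endpoint response

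*SAP*

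**What the plan says.** The primary endpoint is the "proportion of patients with confirmed complete response (CR) or confirmed partial response (PR) as Best" Overall Response (SAP 2.1.3.1), so every BOR rule is a primary-endpoint rule.

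SAP 2.1.3.1 treats new therapy in two ways that agree with each other. It sets the window: "BOR is the best tumor response observed from first study treatment infusion until disease progression, death or initiation of post-treatment anti-cancer therapy", whichever is first. It also states the exclusion: "Tumor assessments after the initiation of post-treatment anti-cancer therapy will be excluded from the determination of Best Overall Response in a patient". It names no exception, but sends the reader to Appendix B for details.

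The closing paragraph of Appendix B does four things in order. It says that assessments after the start of post-treatment anti-tumor therapy are not considered. It defines the therapy date as the earliest of drug, radiation and surgery. It repeats the exclusion: "Assessments performed after the earliest post-treatment anti-tumor therapy will be excluded from the determination of BOR". Finally, for one tumor evaluation period with assessments before the first such therapy, it says that if "several assessments are performed afterwards, the disease assessment will be included in the determination of BOR".

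Two other rules bear on this. On confirmation, Appendix B says "a second tumor assessment with CR or PR at least four weeks later is needed for confirmation". On duration of response, SAP 2.1.3.2.1 censors no later than the start of new therapy: at the last valid assessment before that therapy if it precedes progression or death, and at the therapy date if neither follows.

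**The concern.** The last sentence lets in an evaluation part of which was made after another treatment began, and does not say that only the earlier scans count. Nor does the SAP define a tumor evaluation period, so the span of dates that may be grouped as one evaluation is open. Two programmers could derive different BORs from the same patient's data and each claim to have followed Appendix B.

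The ambiguity favours the drug. A confirming response read partly from scans after surgery, radiation or another drug would be credited to SAR566658. The trial has no control arm in which the same error could occur, and both the Part 1 rule and the final test turn on single responses.

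**Working it through.** **1. Can a straddling evaluation arise?** Yes. SAP 2.5.3 foresees it: "if several scans are performed at different dates for a given tumor evaluation reported in the e-CRF". A therapy start can fall between two such dates.

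**2. Can it confirm a response?** The schedule is: "Tumor assessments will be performed every 6 weeks (ie, every 2 cycles) during the treatment period". Take a patient with a PR at week 6. At week 12 the chest scan is done before new therapy and the abdominal scan after it.

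- Under the exclusion, the later scan is dropped. If target lesions are then missing, SAP 2.5.3 generally makes the time point NE. In SAP Appendix C, PR followed by NE gives SD if the minimum SD duration is met. The patient is not a responder.
- Under the last sentence of Appendix B, read as taking the whole evaluation, week 12 can be a PR. Six weeks exceeds the four required, so the PR is confirmed and the patient is a responder.

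In the second case the confirming scan would fall after the latest date to which SAP 2.1.3.2.1 follows that patient's response if therapy precedes progression.

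**3. Can it create a response alone?** Take SD at week 6 and a first PR in the straddling week 12 evaluation. Confirmation needs a scan at week 16 or later. That scan would normally lie wholly after new therapy and be excluded. Creation would need an evaluation period wide enough to hold two scans at least four weeks apart.

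**4. The plan's own figures.** Inputs from SAP 1.3.2 and section 3: H0 12%, H1 30%, 1-sided alpha 10%, power 80%; 14 patients, then 15 more; stop at 0 or 1 of 14, reject at 6 or more of 14, otherwise reject at 7 or more of 29.

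P(reject) = P(X1≥6) + Σ over x=2 to 5 of P(X1=x)·P(X2≥7−x), with X1 ~ Bin(14,p) and X2 ~ Bin(15,p).

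| Term | p=0.30 | p=0.12 |
|---|---|---|
| X1≥6 | 0.2195 | 0.0038 |
| x=2 | 0.1134×0.4845=0.0549 | 0.2826×0.0265=0.0075 |
| x=3 | 0.1943×0.7031=0.1366 | 0.1542×0.0959=0.0148 |
| x=4 | 0.2290×0.8732=0.2000 | 0.0578×0.2654=0.0153 |
| x=5 | 0.1963×0.9647=0.1894 | 0.0158×0.5524=0.0087 |
| Sum | **0.800** | **0.050** |

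The stated 80% power reproduces. The exact type I error is 5.0%, about half the limit, because the binomial is discrete.

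**5. What one response is worth.** Exact 1-sided p-values at 12%, n=29:

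- 7/29: P(X≥7) = 0.052, reject at 0.10.
- 6/29: P(X≥6) = 0.052 + P(X=6) = 0.052 + 0.075 = 0.127, do not reject.

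In Part 1, one response separates 1/14 (dose not selected) from 2/14 (dose may continue).

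**6. How often would it have to happen?** The documents give no frequency, so this is an assumed range. If a fraction q of true non-responders is counted as responders, the null rate becomes 0.12 + 0.88q, entered in the step 4 formula.

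| q (assumed) | Null rate | Type I error |
|---|---|---|
| 0 | 0.1200 | 5.0% |
| 1% | 0.1288 | 6.9% |
| 2% | 0.1376 | 9.1% |
| 3% | 0.1464 | 11.8% |
| 5% | 0.1640 | 18.1% |

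The 10% limit is reached at q of about 2.35%, which is 29×0.88×0.0235 = 0.6 false responses per 29 patients on average.

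**The case against.** The best defence is that the sentence is a deliberate convention. SAP 2.1.3.1 gives the general rule and defers to Appendix B, which adds a rule for one special case: an evaluation with scans on both sides of the therapy start. Such a convention has a purpose, since scans of one evaluation can have different dates. This stands in part. The sentence may well be an intended exception, but it does not say which scans count, and the BOR window in SAP 2.1.3.1 has no matching exception.

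A reader might infer that post-therapy measurements will certainly enter the sum of diameters. The text does not go that far: it includes the disease assessment and is silent on the individual measurements. For irradiated lesions, other text points the other way. Protocol 8.8 bars an irradiated area from response assessment, though that was written for palliative radiotherapy, which SAP 2.1.8 does not count as post-treatment therapy. The RECIST appendices also say that locally treated lesions are usually not measurable. None of this covers systemic drugs, and it does not clearly settle surgery.

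The strongest point is rarity. Under protocol 10.1.6, a patient who stops for a reason other than progression is not to start further antitumor therapy before progression is documented, and BOR closes at progression. A harmful case therefore needs a departure from that rule, an earlier unconfirmed response, an evaluation spanning the therapy start, and later scans that change the result. This stands as an argument about frequency. It does not repair the rule, and the SAP itself provides for therapy before progression in several endpoint definitions.

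**Conclusion.** The point holds as a flawed rule for the primary endpoint, with low expected frequency. Followed as written, Appendix B allows a post-therapy scan to confirm an earlier CR or PR, which is inconsistent with the BOR window and with the censoring of response duration.

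Two stronger conclusions are not supported. A reader might infer that the sentence lets other treatments create responses outright; the four-week confirmation requirement normally prevents that. A reader might also infer that the type I error exceeds its limit. Nothing in the documents shows this: the exact error is 5.0%, and the 10% limit is passed only if about 2.35% or more of non-responders are miscounted, for which there is no evidence. The contrast between 7/29 and 6/29 shows what any single misclassified response would do; it does not measure this rule's effect.

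The conclusion rests on reading the sentence as including the whole evaluation, which is its plain sense but not its only possible one. The wording should be corrected because the repair is cheap and the error, where it occurs, runs toward counting extra responses.

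**What to change.** Replace the last sentence of Appendix B with, for example: *In an evaluation that straddles the start of post-treatment anti-cancer therapy, only scans dated on or before that start are used. If they are insufficient to determine response under RECIST 1.1, the time point is NE; PD shown on a pre-therapy scan still counts.*

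Also define the tumor evaluation period, and make SAP 2.1.3.1, SAP 2.1.3.2.1 and Appendix B state the same cut-off for new therapy.

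The sample size of 29 and the boundary of 7 do not change. The cost is that an occasional straddling evaluation becomes NE and a confirmation may be lost; under SAP 2.5.3 a patient whose response outcome is non-evaluable counts as a non-responder. That loss is conservative.

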Appendix C Modified Response Evaluation Criteria in Solid Tumors (RECIST 1.1)

Definitions

At baseline, tumor lesions/lymph nodes will be categorized measurable or non-measurable as follows:

Measurable:

- *Tumour lesions*: Must be accurately measured in at least one dimension (longest diameter in the plane of measurement is to be recorded) with a minimum size of:
 - 10 mm by CT scan (CT scan slice thickness no greater than 5 mm).
 - 10 mm caliper measurement by clinical exam (lesions which cannot be accurately measured with calipers should be recorded as non-measurable).
 - 20 mm by chest X-ray.
- *Malignant lymph nodes*: To be considered pathologically enlarged and measurable, a lymph node must be ≥ 15 mm in short axis when assessed by CT scan (CT scan slice thickness recommended to be no greater than 5 mm). At baseline and in follow-up, only the short axis will be measured and followed (see Special Issue 15). See also notes below on “Baseline documentation of target and non-target lesions” for information on lymph node measurement.

Non-measurable

- All other lesions, including small lesions (longest diameter < 10 mm or pathological lymph nodes with 10 to < 15 mm short axis) as well as truly non-measurable lesions. Lesions considered truly non-measurable include: leptomeningeal disease, ascites, pleural or pericardial effusion, inflammatory breast disease, lymphangitic involvement of skin or lung, abdominal masses/abdominal organomegaly identified by physical exam that is not measurable by reproducible imaging techniques.

Special considerations regarding lesion measurability

Bone lesions, cystic lesions, and lesions previously treated with local therapy require particular comment:

Bone lesions:

- Bone scan, PET scan or plain films are not considered adequate imaging techniques to measure bone lesions. However, these techniques can be used to confirm the presence or disappearance of bone lesions.
- Lytic bone lesions or mixed lytic-blastic lesions, with identifiable soft tissue components, that can be evaluated by cross sectional imaging techniques such as CT or MRI can be

considered as measurable lesions if the soft tissue component meets the definition of measurability described above.

- Blastic bone lesions are non-measurable.

Cystic lesions:

- Lesions that meet the criteria for radiographically defined simple cysts should not be considered as malignant lesions (neither measurable nor non-measurable) since they are, by definition, simple cysts.
- “Cystic lesions” thought to represent cystic metastases can be considered as measurable lesions, if they meet the definition of measurability described above. However, if non-cystic lesions are present in the same patient, these are preferred for selection as target lesions.

Lesions with prior local treatment:

- Tumour lesions situated in a previously irradiated area, or in an area subjected to other loco-regional therapy, are usually not considered measurable unless there has been demonstrated progression in the lesion. Study protocols should detail the conditions under which such lesions would be considered measurable.

Methods of measurement

Measurement of lesions: All measurements should be recorded in metric notation, using calipers if clinically assessed. All baseline evaluations should be performed as close as possible to the treatment start and never more than 4 weeks before the beginning of the treatment.

Method of assessment: The same method of assessment and the same technique should be used to characterize each identified and reported lesion at baseline and during follow-up. Imaging based evaluation should always be done rather than clinical examination unless the lesion(s) being followed cannot be imaged but are assessable by clinical exam. Clinical lesions: Clinical lesions will only be considered measurable when they are superficial and 10 mm diameter as assessed using calipers (e.g. skin nodules). For the case of skin lesions, documentation by color photography including a ruler to estimate the size of the lesion is suggested. As noted above, when lesions can be evaluated by both clinical exam and imaging, imaging evaluation should be undertaken since it is more objective and may also be reviewed at the end of the study.

- *Chest X-ray*: Chest CT is preferred over chest X-ray, particularly when progression is an important endpoint, since CT is more sensitive than X-ray, particularly in identifying new lesions. However, lesions on chest X-ray may be considered measurable if they are clearly defined and surrounded by aerated lung.
- *CT, MRI*: CT is the best currently available and reproducible method to measure lesions selected for response assessment. This guideline has defined measurability of lesions on CT scan based on the assumption that CT slice thickness is 5 mm or less. When CT scans have slice thickness greater than 5 mm, the minimum size for a measurable lesion should be twice the slice thickness. MRI is also acceptable in certain situations (eg, for body scans).

- *Ultrasound*: Ultrasound is not useful in assessment of lesion size and should not be used as a method of measurement.
- *Endoscopy, laparoscopy*: The utilisation of these techniques for objective tumour evaluation is not advised. However, they can be useful to confirm complete pathological response when biopsies are obtained or to determine relapse in trials where recurrence following complete response or surgical resection is an endpoint.
- *Tumour markers*: Tumour markers alone cannot be used to assess objective tumour response. If markers are initially above the upper normal limit, however, they must normalise for a patient to be considered in complete response. Specific guidelines for both CA-125 response (in recurrent ovarian cancer) and PSA response (in recurrent prostate cancer), have been published. In addition, the Gynecologic Cancer Intergroup has developed CA125 progression criteria which are to be integrated with objective tumour assessment for use in first-line trials in ovarian cancer.
- *Cytology, histology*: These techniques can be used to differentiate between PR and CR in rare cases if required by protocol (for example, residual lesions in tumour types such as germ cell tumours, where known residual benign tumours can remain). When effusions are known to be a potential adverse effect of treatment (eg, with certain taxane compounds or angiogenesis inhibitors), the cytological confirmation of the neoplastic origin of any effusion that appears or worsens during treatment can be considered if the measurable tumour has met criteria for response or stable disease in order to differentiate between response (or stable disease) and progressive disease.

Tumour response evaluation

To assess objective response or future progression, it is necessary to estimate the overall tumour burden at baseline and use this as a comparator for subsequent measurements. Only patients with measurable disease at baseline should be included in protocols where objective tumour response is the primary endpoint. Measurable disease is defined by the presence of at least one measurable lesion. In studies where the primary endpoint is tumour progression (either time to progression or proportion with progression at a fixed date), the protocol must specify if entry is restricted to those with measurable disease or whether patients having non-measurable disease only are also eligible.

Response Criteria

Table 16 - Evaluation of target lesions

Evaluation of target lesions	
Complete Response (CR)	Disappearance of all target lesions. Any pathological lymph nodes (whether target or non-target) must have reduction in short axis to <10 mm.s
Partial Response (PR):	At least a 30% decrease in the sum of diameters of target lesions, taking as reference the baseline sum diameters.

Evaluation of target lesions

Progressive Disease (PD):	At least a 20% increase in the sum of diameters of target lesions, taking as reference the smallest sum on study (this includes the baseline sum if that is the smallest on study). In addition to the relative increase of 20%, the sum must also demonstrate an absolute increase of at least 5 mm. (Note: the appearance of one or more new lesions is also considered progression).
Stable Disease (SD):	Neither sufficient shrinkage to qualify for PR nor sufficient increase to qualify for PD, taking as reference the smallest sum diameters while on study

Table 17 - Evaluation of non-target lesions

Evaluation of non-target lesions

Complete Response (CR):	Disappearance of all non-target lesions and normalisation of tumour marker level. All lymph nodes must be non-pathological in size (<10 mm short axis).
Incomplete Response/Stable Disease (SD):	Persistence of one or more non-target lesion(s) and/or maintenance of tumour marker level above the normal limits.
Progressive Disease (PD):	Unequivocal progression (see comments below) of existing non-target lesions. (Note: the appearance of one or more new lesions is also considered progression).

Although a clear progression of "non target" lesions only is exceptional, in such circumstances, the opinion of the treating physician. Should prevail and the progression status should be confirmed later on by the review panel (or study chair).

Evaluation of Best overall response

It is assumed that at each protocol specified time point, a response assessment occurs. The following table provides a summary of the overall response status calculation at each time point for patients who have measurable disease at baseline.

Table 18 - Evaluation of overall response

Target lesions	Non-target lesions	New lesions	Overall response
CR	CR	No	CR
CR	Non-CR/non-PD	No	PR
CR	Not evaluated	No	PR
PR	Non-PD or not all evaluated	No	PR
SD	Non-PD or not all evaluated	No	SD
Not all evaluated	Non PD	No	NE
PD	Any	Yes or No	PD
Any	PD	Yes or No	PD
Any	Any	Yes	PD

Table 19 - Evaluation of best overall response

Overall response	Overall response		BEST overall response
	First time point	Subsequent time point	
CR	CR	CR	CR
CR	PR	PR	SD, PD or PR ^a
CR	SD	SD	SD provided minimum criteria for SD duration met, otherwise, PD
CR	PD	PD	SD provided minimum criteria for SD duration met, otherwise, PD
CR	NE	NE	SD provided minimum criteria for SD duration met, otherwise NE
PR	CR	CR	PR
PR	PR	PR	PR
PR	SD	SD	SD
PR	PD	PD	SD provided minimum criteria for SD duration met, otherwise, PD
PR	NE	NE	SD provided minimum criteria for SD duration met, otherwise NE
NE	NE	NE	NE

^a If a CR is truly met at first time point, then any disease seen at a subsequent time point, even disease meeting PR criteria relative to baseline, makes the disease PD at that point (since disease must have reappeared after CR). Best response would depend on whether minimum duration for SD was met. However, sometimes 'CR' may be claimed when subsequent scans suggest small lesions were likely still present and in fact the patient had PR, not CR at the first time point. Under these circumstances, the original CR should be changed to PR and the best response is PR.

The best overall response is determined once all the data for the patient is known.

Best response determination in trials where confirmation of complete or partial response IS NOT required: Best response in these trials is defined as the best response across all time points (for example, a patient who has SD at first assessment, PR at second assessment, and PD on last assessment has a best overall response of PR). When SD is believed to be best response, it must also meet the protocol specified minimum time from baseline. If the minimum time is not met when SD is otherwise the best time point response, the patient's best response depends on the subsequent assessments. For example, a patient who has SD at first assessment, PD at second and does not meet minimum duration for SD, will have a best response of PD. The same patient lost to follow-up after the first SD assessment would be considered invaluable.

Best response determination in trials where confirmation of complete or partial response IS required: Complete or partial responses may be claimed only if the criteria for each are met at a subsequent time point as specified in the protocol (generally 4 weeks later). In this circumstance, the best overall response can be interpreted as in [Table 19](#).

